## Section 3.7 Subject Expenses and Compensation

### Indicate whether or not each of the following applies to this protocol

3.7a) There may be expense or added **costs to the subject** or the subject's insurance.

Yes  No

3.7b) This is a **qualifying cancer treatment trial** and subjects may be billed for study drugs or procedures.

Yes  No

3.7c) This is a cancer treatment trial but **subjects will not be billed** for study drugs or procedures.

Yes  No

3.7d) Subjects will be **compensated** (either in cash or other means such as a gift certificate).

Yes  No

## Section 3.8 Subject Activities

### Indicate whether or not each of the following applies to this protocol

3.8a) Involves **surveys or questionnaires** completed by subjects

Yes  No

3.8b) Includes the use of **recruitment materials** such as flyers, advertisements, or letters

Yes  No

3.8c) Involves facial **photographs** or audio or video **recordings** of patients

Yes  No

## Section 3.9 Sponsors and Collaboration

Indicate whether or not each of the following applies to this protocol

3.9a) This research is a funded research project (**commercial (industry) sponsor, NIH, VA, other**).

Yes  No

3.9b) Other **commercial (industry) non-financial support** is provided (e.g., drugs or supplies).

Yes  No

3.9d) The protocol has **Department of Defense** involvement (e.g., subjects or funding).

Yes  No

3.9c) The PI or other study staff member has a financial interest or other **real or potential conflict** related to this study.

Yes  No

3.9e) This study involves **collaborative** research activities (research conducted at other institutions under the authorities or approvals of the other institution/s). *Note: this may include other VA and/or non-VA institutions, but does not include off-site VA research.*

Yes  No

## Section 4 - Estimated Duration

4) What is the estimated duration of the entire study? (From IRB approval to IRB closure)

5 years

## Section 5 - Lay Language Summary

5) Provide a summary or synopsis of the proposed study using non-technical language (not more than 1 paragraph)

PTSD is prevalent among Veterans and is associated with physical and functional impairments in addition to PTSD symptoms. Veterans with PTSD experience more chronic pain and pain-related functional limitations than Veterans without PTSD. Mind-body interventions such as yoga and meditation are non-pharmacological options for treating both chronic pain and PTSD. This pilot study will add an existing mantram repetition (MR) component designed for Veterans with PTSD to an active yoga intervention known to improve function in chronic back pain patients. The study will examine the acceptability of the interventions, adverse events, and the feasibility of recruitment, attendance, retention, treatment fidelity, and assessments by recruiting and randomizing 32 VA patients with PTSD to either yoga plus MR or to a relaxation/health education control. Health outcomes including pain-related function, pain, and PTSD symptoms will be measured. If feasible, the data will be used to plan a full-scale trial of enhanced yoga for pain in VA patients with PTSD.

## Section 6 - Specific Aims

### 6) Provide a statement of specific aims and hypotheses that serve as the basis for this protocol. Emphasize those aspects that justify the use of human subjects.

In preparation for a full-scale study via a subsequent Merit Review IIR proposal, our overall study objective is to adapt and combine two existing interventions for a new population, and to examine the feasibility and acceptability of conducting a randomized controlled trial of an enhanced yoga + MR mind-body intervention for reducing pain-related disability and pain while improving function in Veterans with PTSD. The study will be conducted in two phases: the first phase will involve adapting and combining two existing mind-body interventions for Veterans with PTSD and chronic pain and creating instructor and home practice manuals for the intervention. The second phase will recruit and randomize 32 military personnel with chronic pain and PTSD to either enhanced yoga (yoga plus MR training) or a relaxation/health education (R/HE) comparison group.

The specific aims are as follows:

Aim 1: Expert collaborators will refine and combine the existing Yoga for cLBP and/or chronic neck pain (cNP) intervention with a shorter version of [name], Repetition Program (MRP).

Aim 2: Create revised instructor and home practice manuals.

Aim 3: Examine the feasibility of recruitment, retention, assessments, randomization, adverse events, and acceptability of an enhanced yoga intervention for reducing disability and chronic pain among Veterans with PTSD via a pilot randomized controlled trial.

## Section 7 - Background and Significance

### 7) Provide a succinct discussion of relevant background information to justify performing the proposed study.

Post-traumatic stress disorder (PTSD) afflicts thousands of Veterans and is associated with a broad array of impairments including physical and functional limitations in addition to PTSD-specific symptoms. Recent research also indicates that Veterans with PTSD are also more likely to report the presence of chronic pain, and they report greater pain severity and pain-related disability than those without PTSD. Mild traumatic brain injury (mTBI) often co-occurs with PTSD and chronic pain, creating complexity for treatment, and more risk of substance use including high-risk opioid use.

Musculoskeletal disorders are the most common type of chronic pain conditions reported by Veterans and chronic low back pain (cLBP) and chronic neck pain (cNP) are two of the most common reasons for disability among deployed personnel and the military in general. Although medications were often a front-line option for pain, the higher risk of addiction in this population and subsequent adverse outcomes including overdose deaths that characterize the US opioid epidemic, have led to increased efforts to study and provide non-pharmacological pain treatments, and reduce long-term opioid therapies in the VA system. Other research points to the potential of treating co-occurring pain and PTSD in the same intervention.

Mind-body interventions are a subset of the non-pharmacological treatment options for pain and PTSD with a growing evidence-base and very few side effects. Considerable evidence suggests that interventions such as Mindfulness Based Stress Reduction (MBSR), and mantram repetition (MR) are effective treatment options for Veterans with PTSD. MBSR has also been shown to reduce disability and improve function in adults with cLBP. Yoga has an even stronger evidence-base for treating CLBP in both Veterans and non-Veterans, and building on preliminary data, is being actively studied as a treatment for PTSD in VA RR&D ([name]) and CSR&D trials ([name]).

Thus, given the enormous health burden of co-occurring pain and PTSD and problems with opioid therapies, we plan to develop a hybrid mind-body intervention to improve function and reduce pain-related disability among Veterans with pain and PTSD in the absence of opioid therapies. The intervention will consist of an established yoga therapy program combined with MR training. MR was specifically chosen because it offers a user-friendly, portable tool for reducing PTSD-related stress and emotional discomfort, and improving function in daily life. Yoga can effectively reduce pain and stress, but is less portable or easily used in public situations such as on public transportation, during traffic challenges, or at the grocery store. MR also adds a personalized spiritual phrase that is not frequently taught in secular yoga or other mind-body programs. Another study innovation is the inclusion of cLBP and cNP. Previous studies rarely combine different pain conditions because the mechanisms of pain may differ and/or too much noise may

be introduced. However, it is increasingly apparent that VA facilities will rarely be able to offer a separate yoga program for each type of pain. Thus, it is increasingly important to study interventions that include more than one type of pain to approximate what will occur in future clinical settings.

## Section 9 - Design and Methods

9) Describe the research design and the procedures to be used to accomplish the specific aims of the project. Provide a precise description of the planned data collection (include what systems or databases will be used/accessed to gather data), analysis and interpretation. For chart review studies, include the timeframe of collection. Address sample size, inclusion of women and minorities. Define in clear terms exactly what will be done to the human subjects.

**C1. Study Design.** The study has three aims. In Aim 1, study investigators will collaboratively modify two existing interventions and combine them into the enhanced yoga intervention. In Aim 2, manuals will be created for both the enhanced yoga intervention and the relaxation/health education (R/HE) control. In Aim 3, we will conduct a preliminary clinical trial to obtain data on the feasibility of recruitment, retention, assessments, randomization, safety, and acceptability of an enhanced yoga intervention for reducing disability and chronic pain among Veterans with PTSD. The proposed study design was chosen in preparation for a full-scale clinical trial. If the interventions are established as safe, acceptable, and it is feasible to conduct necessary study procedures, we will propose a similar design in a subsequent RR&D IIR proposal. The R/HE control was chosen to provide an active control in which participants are exposed to a similar amount of interaction with peers and health professionals, yet the outcomes of interest are not expected to be impacted.

Results dissemination														
Prepare & Apply for IIR														

C1.1. Aim 1 & 2: The interventions will be adapted in four main ways; a) to safely benefit cNP patients; [b) to ensure it is trauma-sensitive; c) includes additional emphasis on relaxation and stress reduction; and d) to include shorter MRP training sessions. Aims 1 and 2 will leverage ongoing work from the PI's current NCCIH-funded R34 in which the yoga for clBP intervention is being adapted to benefit cNP patients. To ensure trauma-sensitivity, study investigators will build on an intervention designed by co-inv. [name] and other study RR&D-funded protocols (Drs. [name] and [name]) to align the intervention with principles outlined by Emerson et al. The additional relaxation and stress reduction emphasis is designed to alleviate PTSD symptoms in addition to chronic pain.] The MRP will be shortened to an initial 30-minute training followed by 15-minute brief interventions sessions and home practice assignments by [name] who has done preliminary work on adapting MRP for briefer sessions and delivery by phone or Internet. Study investigators will review literature, other protocols, and the revised MRP prior to participating in a half-day intervention refinement conference at VASD. Further intervention refinement will occur at project meetings and a manual will be produced.

C1.2. Aim 3: [we will recruit and randomize 32 VA patients formally diagnosed with PTSD and chronic clBP and/or cNP to enhanced yoga or the R/HE control. We plan to recruit starting in month 4, and will begin randomizing when we reach enrollment of 16, which is expected by month 6-7. The first set of interventions will start in month 8 and run for 12 weeks. We will repeat this process with ongoing recruitment of another 16 participants between months 8-12, with interventions running months 13-16. Participants will complete physiological and self-reported outcomes assessments at baseline, 12 weeks, and 18 weeks after enrollment. Assessments will take about 40 minutes each and participants will be compensated \$40 for each completed assessment. We will also conduct qualitative interviews with 7-8 yoga participants and 4-5 R/HE comparison participants to obtain in-depth feedback on satisfaction and areas that could be improved before a larger trial is conducted.] If feasibility, acceptability, and safety are established, the primary health outcome of interest for a subsequent trial is pain-related disability/ functioning (Roland Morris Disability Questionnaire (RMDQ)).

C2. Recruitment. We will recruit a total of [32 Veterans] over the course of 8 months. Co-I [name] serves as Director of Outpatient Mental Health at the Medical Center and meets regularly with providers and the directors of the other mental health clinics, and will orient them to study goals. [name] is Director of the Behavioral Medicine Service and part of the Mental Health Integration Team. She serves as a liaison between mental health clinics and primary care, and also treats and evaluates chronic pain patients. [name] will alert primary care and mental health providers to study goals and criteria. [name] also has experience recruiting chronic pain patients with the help of [name] in primary care clinics and through [name] of the Pain Management service. VA patients will be directly targeted via flyers posted in common areas of VA facilities. In sum, study investigators have extensive experience recruiting PTSD and chronic pain patients at VASD, where ~ 40,000 Veterans have chronic pain, 10-15,000 have PTSD, and 5-6,000 have both conditions. *In-person recruitment will be limited and conducted following RAMP up guidelines, including social distancing, the use of PPE, COVID-19 consent addendum, and COVID-19 symptom screening.*

C3. Screening and Inclusion/Exclusion Criteria. Recruitment staff will conduct a brief pre-screen by phone and schedule interested patients for a screening visit to obtain informed consent and HIPAA authorization. Inclusion/exclusion criteria will be applied using a chart review of the VA medical record, a standard medical history interview, and the screening measures described below. English literacy is required. Participants are asked to not perform other mind-body therapies during the study. *Due to COVID-19 pandemic, procedures have been developed to conduct the formal study clinical screening remotely whenever possible to limit in-person research activities. In-person screening for subjects at normal risk will be conducted following RAMP up guidelines, including social distancing, the use of PPE, COVID-19 consent addendum, and COVID-19 symptom screening.*

C3.1. Inclusion Criteria: age  $\geq$  18, current diagnosis of PTSD in the VA medical record and PCL-5 score of 25 or higher, score of  $\geq$  25 on Montreal Cognitive Assessment (MoCA), willing to reduce or cease opioid medications, willing to attend 12-weeks of yoga and complete 3 assessments. *Due to COVID-19 pandemic, inclusion criteria will be temporarily modified to be age 18 or greater, but less than 65 years of age. Persons 65 or over meeting other inclusion and exclusion criteria will be kept on an list for future consideration but will not be enrolled under current guidance (8/31/20) because of high risk and intervention is not linked to clinical care services.*

C3.2. Exclusion Criteria: serious or unstable psychiatric illness (e.g. psychosis, mania), suicidal or homicidal ideation, < 3 months since major trauma event, moderate or severe cognitive impairment, practiced yoga > 2x in the last 6 months, coexisting medical illness with

yoga contraindicated, affirmative response to any questions on the COVID-19 Pre-Visit Screening Tool.

C3.3 PCL-5. The PCL-5 is a 20-item self-report measure assessing 20 DSM-5 symptoms of PTSD.

C3.4. MoCA is a brief screen for cognitive impairment. We will include those with a score of  $\geq$  25, based on the Youdon index [to ensure that participants are able to understand the informed consent document, their rights as a participant, the assessments, and the intervention instructions.]

C3.5. VA comprehensive suicide screen. Participants will be asked about suicidal thoughts, intent, and behavior, as well as assessment of risk and protective factors as outlined in VA guidelines.

C4. Randomization. After the initial assessment, participants are randomized to either enhanced yoga or the R/HE intervention. Randomization will occur via a web portal linked to a secure file containing two blocks of 20 randomized digits to provide balanced randomization. Research staff will not have access to the file.

C5. Yoga intervention. The existing evidence-based yoga intervention will be adapted to benefit Veterans with cNP, to be more trauma-informed, and to include added relaxation components expected to reduce stress and psychological symptoms of PTSD. Yoga/MR sessions will occur 1x weekly for 12 weeks and the importance of session attendance is emphasized. Participants receive a home practice manual (Appendix 4) containing basic, safe postures that can be performed in ~20 minutes. Instructors can be consulted before or after class about any problems or difficulties encountered. The yoga intervention will be led by [name] who has 10 years of yoga teaching experience, with 7 of those at VASD. [[name] has attended multiple trainings (58 hours) on trauma-sensitive yoga instruction principles, which are a set of adaptations to enhance the comfort of trauma survivors. Trauma sensitive practice includes using **invitational** (as opposed to commanding) language, providing a space where clients feel less **vulnerable** (e.g., lighting should not be too dark), **allowing patients to opt out of postures**, and **minimizing physical assists until trust is established.**] The yoga intervention is classic hatha yoga with Iyengar influences. It uses multiple pose modifications and props to make poses accessible to those limited by health problems and to minimize injury risk. The intervention includes 23 yoga poses performed at a moderate pace. The instruction manual (Appendix 5) has pictures and describes how to perform each pose with typical instructor dialogue. Participants are instructed to take slow, deep breaths in conjunction with specific poses and movement and emulate the postural alignment modeled by the instructor. Each session begins with breathing and meditation followed by 15 minutes of basic postures (Poses 1-8) to warm-up, increase circulation, and increase flexibility. This is followed by a series of standing poses (Poses 9-14) for about 20 minutes. Next, the class transitions to floor poses (Poses 15-22) for about 15-20 minutes. Each session ends with about 10 minutes of relaxation in a supine resting pose or "savasana".

C6. The Mantram Repetition Program (MRP) is a portable meditation-based intervention that has been shown to be effective for treating PTSD and other psychological symptoms/disorders. MRP teaches a set of portable tools, including a) repeating a self-selected "mantram": a word or phrase that provides spiritual strength or meaning for that individual; b) slowing down: refers to slowing down thoughts and raising awareness; also setting priorities so one is not rushed; and c) one-pointed attention: refers to concentrating on one thing at a time instead of "multi-tasking", thereby staying in the present moment and conserving energy. These three tools work together to interrupt negative thoughts and emotional states such as anger, irritability and hyper-arousal, and in turn, improve quality of life. The spiritual focus of the mantram is designed to create personal meaning and inspiration by tapping into inner spiritual resources when the phrase is used. However, religiosity is not emphasized, and participants can choose any phrase that inspires them. The MRP has been manualized (Appendix 6), and the condensed MRP will be taught over the course of 12 weeks. Week 1 will include 30 minutes of MR training, followed by 45 minutes of yoga. Week 2-12 will include about 15 minutes of MR training and dialogue, followed by 60 minutes of yoga. Participants are strongly encouraged to practice MR during daily life, and are asked to self-monitor their use of MR.

C7. Summary of safety information. In multiple full-scale trials of cLBP, and in a broader review of yoga trials, including trials of yoga for cNP, very few adverse events (AEs) have been reported. In studies of yoga for PTSD, no AEs were found when clearly reported. MR studies have not found any AEs attributed to the intervention. If the instructor or research staff become concerned that any participant is at risk of harming him/herself or others, a comprehensive suicide assessment will be performed. If a Veteran is deemed high risk, he/she will be escorted to the walk-in mental health clinic for further treatment.

C8. Relaxation/Health Education intervention. The comparison intervention will be a PTSD health education intervention with added emphasis on specific relaxation techniques. The intervention will be adapted from the Veteran calm (VC) "mind-body intervention" used by co-I [name]. VC was derived from work by Taylor et al. with adaptations to increase its appeal to Veterans. The 12 weekly 75-minute sessions feature psychoeducation about PTSD and the

rationale for relaxation therapy, relaxation techniques (progressive muscle relaxation, imagery), sleep hygiene, applied relaxation, and in-session relaxing experiences (self-massage, chair stretching, sensory experiences). Sessions will be led by experienced health educator.

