**One-leg Stance** - Balance was evaluated using the unipedal stance test, aka the single leg stance. Which is a frequent measure of fall-risk in older adults, but is also frequently used in back pain research. It has been validated and has referenced norms across all adult age groups. The test was administered by research staff with calibrated stopwatches. The participant was instructed to alternately stand on one leg for as long as they could with both eyes open for a maximum of 60 seconds. They were then instructed to repeat the test with both eyes closed.

**C11. Data Analytic Methods.** Because our aims focus on acceptability, feasibility, fidelity and AEs in preparation for a larger RCT, tests of statistical significance are not required. Intervention acceptability and the feasibility of conducting a full-scale RCT will be evaluated using recruitment rates, recruitment to enrollment ratio, intervention attendance rates, retention rates at 12-week assessment, participant satisfaction, serious and non-serious AE rates, participant assessment burden, and instructor fidelity. Mean differences from baseline to follow-up scores will be calculated for outcome measures.

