**C11.2. Data Analysis and Feasibility Criteria.** Recruitment rates will be compared to the specified goal of a mean of 4 enrolled participants per month. We expect to need 5 screened eligible participants per month because some fail to follow through and enroll. If rates remain below 50% of the goal, feasibility will not be established for a full-scale RCT. Attendance rates in many mind-body intervention studies range between 50-80%. For this study, attendance of 50% or higher will be required to support further research on either intervention. A retention rate of 80% or higher is considered an adequate retention rate at a post-intervention assessment for an RCT. Thus, we will use a slightly more lenient 75% or higher retention to indicate feasibility to proceed. Participant satisfaction rates of 75% or higher (measured as % of participants checking agree or strongly agree) will be used to indicate acceptability of the interventions, with little or no modifications needed prior to a larger study. AEs will be evaluated in collaboration with the VASD IRB and the DSMC. In general, any more than 1-2 serious AEs attributed to either intervention among the 20 participants assigned to each would give cause for pausing the intervention until obvious solutions and modifications were identified. Mean time to complete the questionnaires is estimated at 40 minutes. Mean time of 80 minutes or more would indicate burden issues and review of the battery and/or compensation level. Instructor fidelity of under 75% will indicate a need for retraining and/or clarifications of the instructor manual. Finally, mean changes on outcome measures will be compared to minimum clinically important differences where established.

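### Follow-up visits are timed from rolling enrollment, so the 12-week visit used for post-intervention retention usually falls before the course has ended

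*Combined protocol and SAP*

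**What the plan says.** Section 9, C1.2 (Aim 3) holds the only legible visit schedule: "Participants will complete physiological and self-reported outcomes assessments at baseline, 12 weeks, and 18 weeks after enrollment". The same paragraph sets the trial calendar:

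- **Cohort 1.** Recruitment starts in month 4, and the team "will begin randomizing when we reach enrollment of 16, which is expected by month 6-7". Then: "The first set of interventions will start in month 8 and run for 12 weeks".
- **Cohort 2.** There is "ongoing recruitment of another 16 participants between months 8-12, with interventions running months 13-16".

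C2 adds: "We will recruit a total of [32 Veterans] over the course of 8 months". C5 gives the length of the yoga course: "Yoga/MR sessions will occur 1x weekly for 12 weeks". C8 gives the control arm 12 weekly sessions as well.

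Two later sections rely on the 12-week visit. C11 lists "retention rates at 12-week assessment" among its feasibility measures. C11.2 takes 80% as an "adequate retention rate at a post-intervention assessment for an RCT" and from it derives the trial's more lenient 75% threshold. C11.2 also compares mean changes on the outcome measures with minimum clinically important differences.

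**The concern.** C1.2 treats enrollment as something that happens one person at a time, before randomization and before a class start shared by the whole cohort. A visit 12 weeks after enrollment cannot also follow a 12-week course unless the person enrolls about when classes begin. So one visit is given two meanings: 12 weeks after enrollment in C1.2, and after the intervention in C11 and C11.2.

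If staff booked visits by the written rule, two results would suffer:

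1. **Retention.** This is one of the few numeric criteria for proceeding to a full trial. It would be counted mid-course, or before any class, and would not be the post-intervention retention it is benchmarked to.
2. **Mean change.** The changes set against minimum clinically important differences would mix people with no treatment, part of the course and all of it.

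The second comparison is descriptive. Attendance has its own sign-in logs and its own 50% criterion, so poor attendance would still be seen. Nothing here bears on adverse events, fidelity or satisfaction.

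**Working it through.** **The plan's own pace.** 32 participants / 8 months (C2) = 4 per month, which is the goal in C11.2. At that pace 16 / 4 = 4 months, so a month 4 start fills cohort 1 by the end of month 7. This agrees with the expected month 6-7.

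**Inputs from the documents.** 16 per cohort; enrollment from month 4 to month 6-7, then months 8-12; courses starting in months 8 and 13; 12 weekly sessions; visits at 12 and 18 weeks.

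**Assumptions.** Enrollment is spread evenly over each window (16 equally spaced midpoints), with 4.348 weeks per month. The documents give only windows, so the windows and the class start day are varied.

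**Formulas.** Wait = class start - enrollment date. Session k takes place k - 1 weeks after session 1, so session 12 is at week 11. A visit at week t:

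- precedes session 1 if wait > t;
- precedes session 12 if wait + 11 > t, which means wait > 1 for the 12-week visit and wait > 7 for the 18-week visit;
- has floor(t - wait) + 1 sessions behind it, limited to 0-12.

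**Lead case: months 4-6 and 8-12, classes on the first day of months 8 and 13.** This split fits both the windows in C1.2 and the 8 months in C2.

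- Cohort 1: the window is 3 x 4.348 = 13.04 weeks, so spacing is 13.04 / 16 = 0.815 weeks. Month 8 opens 4 x 4.348 = 17.39 weeks after month 4 does. Longest wait 17.39 - 0.815/2 = 17.0 weeks; shortest 17.39 - 13.04 + 0.815/2 = 4.8; mean 10.9.
- Cohort 2: the window is 5 x 4.348 = 21.74 weeks, so spacing is 1.359 weeks. Longest wait 21.74 - 1.359/2 = 21.1 weeks; shortest 0.7; mean 10.9.
- 12-week visit before session 1 (wait > 12): 7 + 7 = 14 of 32 (44%).
- 12-week visit before session 12 (wait > 1): 16 + 15 = 31 of 32 (97%). Mean sessions held: 3.0.
- 18-week visit before session 12 (wait > 7): 13 + 11 = 24 of 32 (75%).

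**All scenarios** (counts out of 32; the split is months of accrual in cohort 1 + cohort 2)

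| Class start | Split | 12-wk before session 1 | 12-wk before session 12 | Mean sessions at 12 wk | 18-wk before session 12 |
|---|---|---|---|---|---|
| First day | 4+4 | 10 | 30 | 4.5 | 20 |
| First day | 4+5 | 12 | 30 | 4.0 | 21 |
| First day | 3+4 | 12 | 31 | 3.5 | 23 |
| First day | 3+5 | 14 | 31 | 3.0 | 24 |
| Mid-month | 4+4 | 14 | 32 | 3.1 | 24 |
| Mid-month | 4+5 | 16 | 32 | 2.8 | 24 |
| Mid-month | 3+4 | 16 | 32 | 2.2 | 27 |
| Mid-month | 3+5 | 18 | 32 | 1.9 | 27 |

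Placing the course end at week 12 instead of at session 12 (week 11) would put the 12-week visit before it for everyone enrolled ahead of the first class. The table uses the more cautious convention.

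**If enrollment means randomization.** Sessions held by the 12-week visit = floor(12 - gap) + 1, limited to 12, where gap is the weeks from randomization to session 1. This gives 12 sessions with a gap of up to 1 week, 11 with 2 weeks, 8 with 4.3 weeks (one month) and 4 with 8.7 weeks (two months). The 18-week visit precedes session 12 only if the gap exceeds 7 weeks.

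**The case against.** The strongest reply is that the intent is clear. Both courses last 12 weeks, C11 puts retention at 12 weeks, and C11.2 speaks of a post-intervention assessment, so the 12-week visit must be the end-of-course visit. The literal rule is also barely workable. Under the same even-accrual model, about 8 of 32 people (3+5 or 4+4 split) would reach 12 weeks before their cohort had its 16th enrollee, so before randomization if it waits for that person. Enrollment is not defined, the phrase about enrollment might attach only to the 18-week visit, and the timeline table in C1 survives only in part. The lead case is also the harshest of the four first-day splits; 4+4 matches the goal of 4 per month better, although it leaves out month 8 of the second window.

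Much of this is fair. The intent is probably a course clock, the damaged table neither supports nor excludes one, and the counts illustrate the written rule; they do not forecast the trial. But C1.2 makes an enrollment of 16 the trigger for randomizing, so its own wording separates the two events. If the phrase covers only the 18-week visit, the 12-week visit has no stated anchor, and the 18-week visit still precedes session 12 in 20-27 of 32. The milder 4+4 split still puts 30 of 32 12-week visits before session 12 with a first-day start. A probable intent makes the correction easy; it does not make the sentence right.

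**Conclusion.** The concern holds. The stated visit rule conflicts with the use made of the 12-week visit in C11 and C11.2. Read literally, with even accrual, the 12-week visit precedes the last session in 30-32 of 32 participants and the first session in 10-18 of 32. On average 3.0-4.5 of 12 sessions have been held with a first-day class start, or 1.9-3.1 with a mid-month start.

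The size rests on the assumed accrual pattern and start dates, and on enrollment meaning the event that precedes randomization. On the randomization reading it depends on a gap that the documents do not fix. No hypothesis test depends on visit timing, since none is planned. The point should be fixed because a criterion for going on to a full trial depends on it. Confidence is medium, given the probable intent and the incomplete timeline table.

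**What to change.** In C1.2, time the two follow-up assessments from the cohort's course: the first in the week after the cohort's last scheduled session, the second 6 weeks later. With no pause this equals 12 and 18 weeks after the first session. Section 9.9 allows research activities to cease, so the sentence should also say that the date moves with a rescheduled last session; the first follow-up then stays post-intervention. In C11 and C11.2, state that the 75% retention criterion applies to this end-of-course assessment.

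The cost is one sentence in C1.2, one clause in C11/C11.2 and rescheduled visits, with no added participants or visits. There are two downsides. Follow-up dates are no longer known at enrollment. And if baseline is done at enrollment, it would precede the first class by about 17-21 weeks for the earliest enrollees (first-day start). That gap comes from the existing enrollment plan; whether to repeat baseline is a separate choice.
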